6 ANALYSIS SETS/ POPULATIONS

6.1 ALL PATIENT SET

The All Patient Set (ALL) includes all patients enrolled in the study and will include all data collected at both scheduled and unscheduled visits. The ALL will primarily be used for disposition analyses and listings.

6.2 FULL ANALYSIS SET

The Full Analysis Set (FAS) will include all patients who receive at least one dose of tofacitinib and have at least one post-baseline visit. The primary analysis will use the FAS. The FAS will include all data collected during the study, both scheduled and unscheduled visits.

The protocol states that patients will be enrolled if they fulfil all selection criteria for the study and are started on treatment with tofacitinib for moderate to severely active rheumatoid arthritis.

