7.9.1. Analysis Populations

The Full Analysis Set is defined as patients who receive at least one dose of Tofacitinib and have at least one set of post-baseline measurements. This population will be used for all efficacy analysis. Details of any methods employed to deal with missing data will be outlined in the SAP.

The Safety Analysis Set is defined as all patients who receive at least one dose of Tofacitinib. This population will be used for all safety analysis.

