8.2. Patient withdrawal

Patients may withdraw from the study at any time at their own request, or they may be withdrawn at any time at the discretion of the HCP or sponsor for safety, behavioural, or administrative reasons. In any circumstance, every effort should be made to document subject outcome, if possible. The HCP should inquire about the reason for withdrawal and follow-up with the patient regarding any unresolved adverse events. The further treatment of a patient is independent from his/her withdrawal.

If the patient withdraws from the study, and also withdraws consent for disclosure of future information, no further evaluations should be performed, and no additional data should be collected. The sponsor may retain and continue to use any data collected before such withdrawal of consent.

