6.3 SECONDARY FULL ANALYSIS SET

Patients with data collected while taking tofacitinib will be assigned to the Secondary Full Analysis Set (SFAS) at a given time point, which will be used for all secondary endpoint analyses. A patient is considered on tofacitinib at a given timepoint if the patient has not terminated or paused tofacitinib at the time of the visit or event. Termination or pauses are documented in eCRF instrument “Rheumatologische Medikation” for therapy class tsDMARD/bDMARD, where variable *Change* (BDCM.CHANGECD) is set to “Therapy stop” = termination or set to “Therapy paused” = pause.

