6.4 SAFETY ANALYSIS SET

The Safety Analysis Set (SAS) will consist of all patients who receive at least one dose of tofacitinib. All reporting of safety data will utilize the SAS.

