9.2.3.10 DRUG SURVIVAL STATUS OF TOFACITINIB

Time to cease taking tofacitinib (drug survival) will be analysed as per Section 9.1.2, using the SFAS. Missing data will not be imputed (as per Section 8.1).

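### Drug survival is assigned to two different analysis sets, and under the FAS a treated patient with a recorded stop but no post-baseline visit is dropped, which biases persistence upward

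*SAP*

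**What the plan says.** SAP 6.2 defines the FAS as "all patients who receive at least one dose of tofacitinib and have at least one post-baseline visit". It also says that "The FAS will include all data collected during the study, both scheduled and unscheduled visits", so an unscheduled visit is enough for entry. Protocol 7.9.1 (Analysis Populations) has a similar rule: patients must have had a dose and "have at least one set of post-baseline measurements. This population will be used for all efficacy analysis".

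The SAP names two different sets for drug survival:

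- SAP 6.3 introduces the SFAS, "which will be used for all secondary endpoint analyses", and SAP 9.2.3.10 repeats this for the endpoint itself: "Time to cease taking tofacitinib (drug survival) will be analysed as per Section 9.1.2, using the SFAS". The SFAS is built from data recorded while the patient is on tofacitinib, judged at each time point. Its definition states no post-baseline-visit rule.
- The drug survival row of summary table 9.2.6 names the FAS.

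SAP 7.1.2.10 defines the endpoint. The event is a therapy stop recorded for tofacitinib, and time runs from the initiation date to the termination date. Patients who withdraw or are lost to follow-up are censored at their last visit.

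A set without the visit condition already exists: "The Safety Analysis Set (SAS) will consist of all patients who receive at least one dose of tofacitinib" (SAP 6.4). It is assigned to safety reporting only.

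**The concern.** Drug survival is measured from the start of tofacitinib and needs two dates, initiation and termination. No post-baseline measurement enters the calculation. The FAS nevertheless makes entry depend on something that happens after time zero, namely attending a later visit. The first scheduled follow-up has target day 91 (SAP 12.1.1), and the protocol makes no visit mandatory.

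Take two treated patients with the same recorded stop date before Month 3. One returns once, enters the FAS and counts as an event on the true date. The other does not return and disappears from the analysis. The patients removed in this way are all early failures, so the bias has one direction: reported persistence at 12 and 24 months (Protocol 6.1.2, item j) is too high.

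The conflict between the two sets makes this worse. The SFAS does not impose the visit rule, but a set that asks whether a patient is still on drug at the time of a visit or event is an awkward basis for an endpoint whose event is stopping the drug. The SAP therefore does not say clearly which treated patients are in the risk set.

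**Working it through.** The plan gives no persistence rate, early-dropout rate or precision target for drug survival, so there is no figure of its own to reproduce. The check is an identity with assumed inputs.

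**Inputs.** From the documents: planned N of about 1500 (Protocol 7.2); event and censoring rules (SAP 7.1.2.10); FAS rule (SAP 6.2); first follow-up target day 91 (SAP 12.1.1). Assumed, because the documents do not give them: f, the share of all treated patients with a recorded stop and no post-baseline visit; and S_FAS, drug survival in the FAS.

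**Step 1, formula.** The excluded patients all fail early. If no FAS patient is censored before the last of those stops, then at any later time

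S_all = (1 - f) × S_FAS, so overstatement = S_FAS - S_all = f × S_FAS.

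With some early censoring in the FAS the relation is approximate.

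**Step 2, range (overstatement in percentage points).**

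| f (assumed) | S_FAS = 30% | S_FAS = 50% | S_FAS = 70% |
|---|---|---|---|
| 1% | 0.3 | 0.5 | 0.7 |
| 2% | 0.6 | 1.0 | 1.4 |
| 5% | 1.5 | 2.5 | 3.5 |
| 10% | 3.0 | 5.0 | 7.0 |

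For example, at f = 5% and S_FAS = 50%: 0.95 × 0.50 = 0.475, which is 2.5 points lower. For scale, the 95% half-width at N = 1500 and S = 50% is 1.96 × √(0.25/1500) = 0.0253, about 2.5 points.

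**Step 3, Kaplan-Meier simulation.** N = 1500 with 75 early leavers (5%). Their stop dates lie between day 1 and day 90; all others persist to day 91 and then stop at a constant hazard.

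| Assumed hazard | Month | FAS | Early stops counted as events | Early leavers censored at baseline |
|---|---|---|---|---|
| higher | 12 | 60.4% | 57.4% | 60.4% |
| higher | 24 | 30.0% | 28.5% | 30.0% |
| lower | 12 | 74.7% | 71.0% | 74.7% |
| lower | 24 | 52.9% | 50.3% | 52.9% |

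The fourth column agrees with 0.95 × FAS throughout. The last column shows the other half of the result. A patient with no recorded stop date is censored at the last visit. If that visit is baseline, the patient leaves the risk set at time zero and the curve does not move.

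**Step 4, time to first escalation.** Table 9.2.6 puts this endpoint on the FAS too, so it was checked in the same way. Its event is a step-up (SAP 7.1.2.1). Stopping without starting a new DMARD is a termination under SAP 7.1.1, not a step-up. A patient who simply stops and leaves would be censored at baseline, and including that patient changes the estimate by 0. Only a switch to a new DMARD that is documented without any visit would be lost.

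**The case against.** The strongest reply is that the affected group may be very small, or empty.

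- **The governing text may be the SFAS.** SAP 6.3, 9.2.3 and 9.2.3.10 agree with each other, and the SFAS carries no visit rule. This stands in part: the exclusion is certain only if table 9.2.6 and Protocol 7.9.1 govern. A reader might infer that the SFAS drops the same patients, but its definition does not say so.
- **A stop date without a visit may rarely exist.** Protocol 7.6.5 ties treatment documentation to visits. Protocol 8.2 says only that "every effort should be made to document subject outcome, if possible", which is a request for outcome and not for a tofacitinib stop date. This stands as a limit on size. Such a record is still possible, because serious events and lack of efficacy are reportable within 24 hours of awareness, independently of visits (Protocol 9.1). One cannot assume, however, that the stop dates of these patients are already in the database.
- **Few patients lack any later visit.** Unscheduled visits count for the FAS. Patients who stop tofacitinib stay under observation unless they leave the study (Protocol 7.5.1.4), and a close-out visit is provided for. This also stands. A patient who stops before Month 3 and returns once is kept as an event on the true date, so it would be wrong to infer that FAS membership guarantees persistence to the first visit.
- **Disclosure is partly planned.** SAP 9.2.1 reports numbers per time point and reasons for withdrawal. That helps, but it neither singles out treated patients with no post-baseline visit nor corrects the curve.

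None of this explains why a measure of persistence from first dose should require a later visit.

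**Conclusion.** The point holds for drug survival, in a limited form. The SAP names two sets for one endpoint. Under the one given in table 9.2.6 and Protocol 7.9.1, a treated patient with a documented stop and no post-baseline visit is removed. The bias can only be upward.

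Its size is f × S_FAS. Because f is unknown, the documents do not show that the bias is material: at an assumed S_FAS of 50% it is 0.5 points at f = 1% and reaches the width of the sampling error, 2.5 points, at f = 5%. It is zero for patients without a recorded stop date, so changing the set alone does nothing for them.

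Two stronger readings are not supported. A reader might infer that time to first escalation is biased to the same degree; it is touched only where a switch to a new DMARD is documented without a visit. A reader might also count a death before the first visit as a lost drug-survival event; SAP 7.1.2.10 lists a recorded therapy stop as the event and does not mention death.

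Drug survival is a descriptive secondary endpoint in a single cohort, and the primary covariate model is not in question here.

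**What to change.** 1. In SAP 9.2.3.10 and table 9.2.6, name one set for drug survival: all patients with at least one dose of tofacitinib, which is the existing Safety Analysis Set definition. Align SAP 6.3 and note the departure from Protocol 7.9.1.
2. State that a documented stop before any follow-up visit is an event at its recorded date.
3. Report the number of treated patients with no post-baseline visit, with reasons, split by whether a stop date is recorded.
4. Add a sensitivity analysis that treats those without a recorded stop date as early stops. If they are a share g of treated patients, this gives (1 - f - g) × S_FAS, a lower bound to set beside the main estimate.
5. Keep the FAS for the recurrent-event covariate model, where post-baseline values are needed.

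The cost is mainly SAP wording, one extra disposition line and one extra Kaplan-Meier run. Some stop dates may have to be queried with sites before database lock, since routine capture is tied to visits. The downside is that reported persistence becomes slightly less favourable.

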6.3 SECONDARY FULL ANALYSIS SET

Patients with data collected while taking tofacitinib will be assigned to the Secondary Full Analysis Set (SFAS) at a given time point, which will be used for all secondary endpoint analyses. A patient is considered on tofacitinib at a given timepoint if the patient has not terminated or paused tofacitinib at the time of the visit or event. Termination or pauses are documented in eCRF instrument “Rheumatologische Medikation” for therapy class tsDMARD/bDMARD, where variable *Change* (BDCM.CHANGECD) is set to “Therapy stop” = termination or set to “Therapy paused” = pause.

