7.1.2.10 DRUG SURVIVAL STATUS OF TOFACITINIB

For patients who terminate tofacitinib, the drug survival status will be recorded as follows:

Those who terminate tofacitinib:

- Status = 1
- Time = Termination date tofacitinib – Date of initiation on tofacitinib

Tofacitinib is terminated when indicated on instrument “Rheumatologische Medikation” for therapy class tsDMARD/bDMARD variable *Change* (BDCM.CHANGECD) is set to “Therapy stop”. Tofacitinib pauses, where variable *Change* is set to “Therapy paused”, are not considered terminations.

Patients who do not terminate tofacitinib:

- Status = 0
- Time = Date of final visit – Date of initiation on tofacitinib

If patient is lost to follow-up or withdraws from the study they will be censored at the date of their last visit.

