9.1.6 COMPARISON BETWEEN TREATMENTS

As there is only one cohort, those who are initiated on tofacitinib, there will be no formal comparison between treatment groups, although endpoints may be summarised by treatment subgroups (Section 6.6). All descriptive statistics will be presented overall and for all secondary analyses this will only be done using the data recorded when patients were taking tofacitinib.

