9.2.3 SECONDARY ANALYSES

All secondary endpoints will be analysed using the SFAS.

Other subgroup analyses maybe carried out, these will be defined prior to database lock.

NOTE: Although a subject will be included in the analysis set regardless of their sequence of treatment, only data collected while a subject was on tofacitinib will be included in the secondary analyses. Methods used are described in Section 9.1.2 - 9.1.4.

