9.2.3.1 TIME TO FIRST TREATMENT ESCALATION

Time to first treatment escalation will be analysed as in Section 9.1.2 using the SFAS. Missing or incomplete dates will not be imputed (as per Section 8.1).

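### Drug survival and time to first escalation are assigned to the SFAS in the SAP text but to the unrestricted FAS in table 9.2.6, and the SFAS rule taken literally removes the events

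*SAP*

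**What the plan says.** **Analysis set in the text.** SAP 9.2.3 states a general rule, "All secondary endpoints will be analysed using the SFAS", and its note adds that "only data collected while a subject was on tofacitinib will be included in the secondary analyses". The rule is repeated for each of the two endpoints: "Time to first treatment escalation will be analysed as in Section 9.1.2 using the SFAS" (9.2.3.1) and "Time to cease taking tofacitinib (drug survival) will be analysed as per Section 9.1.2, using the SFAS" (9.2.3.10). SAP 9.1.6 restates the restriction for descriptive statistics: "for all secondary analyses this will only be done using the data recorded when patients were taking tofacitinib".

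**Definition of the SFAS.** Under SAP 6.3 a patient is on tofacitinib at a given time point "if the patient has not terminated or paused tofacitinib at the time of the visit or event".

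**Analysis set in the table.** Table 9.2.6 lists the FAS alone for Time to First Treatment Escalation and for Drug Survival. The rows for LDA, remission and the change-from-baseline endpoints also say FAS, but they add a restriction to on-tofacitinib data. The two time-to-event rows carry no such addition.

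**Events.** For drug survival, SAP 7.1.2.10 reads "For patients who terminate tofacitinib, the drug survival status will be recorded as follows", with Status = 1 at the termination date. Pauses "are not considered terminations". For time to first escalation (SAP 7.1.2.1) the event is a step-up. By 7.1.1 and table 12.2 this includes stopping tofacitinib and starting another agent.

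**Summaries.** SAP 9.1.2 lists mean, SD, median, minimum and maximum, and a Kaplan-Meier plot described as one of the hazard function. Protocol 7.9.2.2.1 asks for Kaplan-Meier methods with medians and confidence intervals. Protocol 6.1.2 (j) asks for drug survival at months 12 and 24.

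**The concern.** For LDA, remission and change scores, restricting to on-tofacitinib data is coherent: the endpoint is a status measured while the patient takes the drug. For these two endpoints it is not, because the event is itself, or usually coincides with, the end of tofacitinib. A filter that asks whether the patient is still on the drug at the time of the event selects on the outcome.

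The SAP gives both instructions, so two programmers could each follow it and produce different retention and step-up curves. The error has a direction: the SFAS reading makes retention look better and step-up look rarer. The same methods were applied in the interim analyses (SAP 4.1), and the protocol plans to present interim results at congresses (10.1).

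**Working it through.** The documents give no figure for either endpoint, so there is nothing to reproduce. The check applies the SFAS rule to each event definition and then sizes the effect under assumed rates.

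**1. Drug survival.** The event is termination at its own date. At that date tofacitinib is terminated, so the SFAS condition fails for every event. The event count is 0 and the Kaplan-Meier curve stays at 100%. A simulation with N = 1500 and assumed 24-month termination of 20%, 40% or 60% gave:

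| Assumed termination | FAS events | FAS 24-month survival | Literal SFAS events | Literal SFAS survival |
|---|---|---|---|---|
| 20% | 301 | 79.9% | 0 | 100% |
| 40% | 626 | 58.3% | 0 | 100% |
| 60% | 900 | 40.1% | 0 | 100% |

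**2. Which step-ups survive the rule.** In table 12.2 the rows for tofacitinib alone and for tofacitinib with a csDMARD each show 6 step-up cells in the extracted text. In each row 5 of the 6 replace tofacitinib. Counted by column heading it is 7 cells, 6 of them replacing, because one cell per row seems to have been lost in extraction. Only adding a csDMARD, or exchanging it while tofacitinib continues, is kept. These are counts of regimen types, not shares of events.

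**3. Size for time to first step-up.** Let F be the true 24-month step-up proportion and p the share that replaces tofacitinib. Assume constant hazards, with replaced patients censored instead of counted. The hazard falls by the factor (1 − p), so the reported proportion is 1 − (1 − F)^(1 − p). Example: F = 0.5 and p = 0.5 give 1 − 0.5^0.5 = 0.293.

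| True F | p = 0.25 | p = 0.50 | p = 0.75 |
|---|---|---|---|
| 30% | 23.5% | 16.3% | 8.5% |
| 40% | 31.8% | 22.5% | 12.0% |
| 50% | 40.5% | 29.3% | 15.9% |
| 60% | 49.7% | 36.8% | 20.5% |

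A simulation that censored at the last quarterly visit on tofacitinib agrees: 23.3% and 12.1% for F = 40% with p = 0.50 and 0.75.

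**4. Pauses.** Suppose terminations count but data are cut at a pause. Let h be the stopping hazard before a pause, r·h the hazard after it, and g the pause hazard. The curve cut at pauses is exp(−ht). The true curve is exp(−(h+g)t) + ∫₀ᵗ g·exp(−(h+g)u)·exp(−rh(t−u)) du. Set g so that 10–30% would pause over 24 months, and solve h so that true 24-month retention is 40–60%:

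- r = 1: no difference.
- 10% pausing, r = 2: retention overstated by 1.3–1.4 percentage points at month 24.
- 30% pausing, r = 3: overstated by 6.6–7.2 points at month 24 and by 2.4–3.4 points at month 12.

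**5. Mean against median.** With exponential stopping, no dropout and follow-up ended at 24 months, the mean of observed times is (1 − R)/λ, where R is 24-month retention and λ = −ln(R)/24. For R = 0.6, λ = 0.0213 per month, the mean is 0.4/λ = 18.8 months and the true median is ln 2/λ = 32.6 months. That lies beyond follow-up, so the Kaplan-Meier median is not reached while a mean is still printed. For R = 0.4 and 0.5 the means are 15.7 and 17.3 months against true medians of 18.2 and 24.0.

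**The case against.** **The endpoint definitions are more specific than the SFAS rule.** SAP 7.1.2.10 codes termination as Status = 1, and 7.1.2.1 codes a step-up the same way. A patient is at risk until the stop, and a drug-survival curve with no events would be noticed at once. This stands: a flat curve is unlikely to be published. It does not settle the matter, because even a lenient reading that keeps events up to the stop date loses a replacement step-up dated after it, and it leaves pauses open.

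**The pause effect may be nothing.** It is zero unless stopping is faster after a pause, and no document gives a pause rate. This stands as to size. The inconsistency between 6.3 and 7.1.2.10 remains.

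**The summary criticism is partly answered elsewhere.** SAP 5 promises confidence intervals in general, the table shells are in a separate document, and with no dropout the mean of observed times is a legitimate restricted mean over 24 months. The shells may indeed hold the month 12 and 24 estimates. But 7.1.2.10 provides for loss to follow-up and withdrawal. With dropout the plain mean and SD no longer describe the time to event, and 9.1.2 still departs from the protocol's wording.

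**The FAS has its own exclusion.** It requires a post-baseline visit, which SAP 6.3 does not ask of the SFAS. This is true, but such patients contribute almost no follow-up.

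**Conclusion.** The concern holds. The SAP text and table 9.2.6 name different analysis sets for these two endpoints, and the SFAS condition applied as written removes the drug-survival event and the step-ups that replace tofacitinib. The conflict rests on the text alone and needs no assumed rate.

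The size does rest on assumptions. For true 24-month step-up of 30–60% with 25–75% of step-ups replacing tofacitinib, the literal rule would report 8.5–49.7%. Cutting follow-up at pauses would overstate retention by 0 to about 7 percentage points at month 24 and 0 to about 3 at month 12.

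The point should be fixed before the final analysis. It is not critical: both endpoints are secondary and descriptive, and the primary analysis uses the FAS and is untouched.

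**What to change.** - **9.2.3.1 and 9.2.3.10:** name the FAS, in line with table 9.2.6 and with protocol 7.9.1, which uses the FAS for all efficacy analysis.
- **6.3, 9.2.3 and 9.1.6:** exempt these two endpoints from the SFAS and from the on-tofacitinib restriction. State that an event on or at the stopping of tofacitinib counts.
- **Pauses:** state that in the drug-survival analysis a pause is neither an event nor the end of follow-up, consistent with 7.1.2.10.
- **9.1.2:** replace the mean, SD, median, minimum and maximum with the Kaplan-Meier median and its 95% confidence interval, and describe the plot as the survival function.
- **Drug survival:** add Kaplan-Meier estimates with 95% confidence intervals at months 12 and 24.

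The cost is SAP wording. The estimates come from the Kaplan-Meier procedure already planned. Reported retention may look less favourable and step-up more frequent. Because the interim analyses used the same methods, the final report should say which set those runs used, so that any difference from interim results can be explained.
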